We will address the following specific aims (*primary outcomes): (1) Test the sustained effects (baseline, 3 months (2 weeks post intervention), 6 and 12 months) of CBT-I provided in 4 group sessions over 8 weeks, compared with HF self-management education (attention control condition), on: (1a) *insomnia severity and self-reported and actigraph-recorded sleep characteristics (*sleep quality, *sleep efficiency, sleep latency, and duration); (1b) symptoms (*fatigue, anxiety, depression, pain, dyspnea, sleepiness, sleep-related impairment), and psychomotor vigilance (PVT); and (1c) symptom clusters [membership in clusters characterized by severity of specific symptoms; transition between clusters over time]; (2) Test the sustained effects of CBT-I on self-reported and objective functional performance; and (3) Examine the cost-effectiveness of CBT-I.

Exploratory aim: We will explore the effects of CBT-I on event-free survival.

Hypotheses: CBT-I, compared with an attention-control condition (HF self-management education), leads to: (1a) decreased insomnia severity and sleep latency and increased sleep quality, duration and efficiency that are sustained at 6, and 12 months; (1b) decreases in severity of symptoms and improvements in psychomotor vigilance that are sustained at 6, and 12 months; and (1c) transition between symptom clusters that have higher symptom severity to those that have lower symptom severity over time. (2) CBT-I will lead to increased self-reported and objective functional performance; (3) CBT-I is cost-effective, compared with HF self-management education alone.

Support for the proposed hypotheses will lead to future research focused on the dissemination and translation of CBT-I into diverse HF settings. Increased access to CBT-I has high potential to improve HF patients' ability to self-manage sleep and daytime symptoms and decrease the costs of health care resource utilization.

RESEARCH STRATEGY

Significance. This study is responsive to PA 14-344 “Self Management for Health in Chronic Conditions” and NINR’s strategic plan.³⁰ Our study will address the dearth of efficacious self-management interventions for patients who have co-occurring conditions, specifically comorbid chronic insomnia and HF.

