Week 1: Session 1	Overview of symptoms of HF and HF self-management; Weight & symptom monitoring; Sleep education: overview of CBT-I; sleep stages; circadian rhythm; role of HF & treatment in sleep; Sleep scheduling/restriction; Stimulus Control	Overview of symptom of HF and HF self-management; definitions of HF; Signs & Symptoms and their meaning; Weight & symptom monitoring; Diagnostic Testing; Medical contact form
Week 3: Session 2	Review sleep diaries; Adjust sleep schedule; Education: Physiological arousal/fight or flight vs. relaxation response; Cognitive restructuring; Relaxation training; Optional Hypnotic taper	Review progress & homework; HF symptom management: Fluid and sodium Management; Effective communication w/ healthcare providers
Week 5: Session 3	Adjust sleep schedule; Review previous strategies; Lifestyle factors/sleep hygiene: exercise, sleep environment, food, alcohol caffeine; “Mini” relaxation	HF Medications & Strategies to promote adherence; OTC medications/herbal remedies; Cardiac devices
Week 7: Session 4	Reinforce adherence/Call attention to progress/review; Relapse prevention advice	Healthy Lifestyle: Diet: Lipids, sodium, Calories; CVD risk factors; Stress Management/relaxation; Exercise; Environment and sleep; Review

*Telephone calls weeks 2, 4, 6, 8

Month), had standard evidence-based HF disease management,³⁵ concerns about insomnia for \geq one month; scored ≥ 8 on the Insomnia Severity Index,¹⁰⁴ and had no-mild untreated SA or were adherent to SA treatment. We randomized to HH or HS in groups of 5, obtained self-reports of insomnia/sleep, symptoms and functional performance and 2 weeks of wrist actigraphy/diaries; provided HS/HH interventions; and repeated full assessment at 2 weeks post-intervention (T1). Self-report measures included the Insomnia Severity Index, Pittsburgh Sleep Quality Index, Centers for the Epidemiological Studies of Depression Scale, Spielberger State Anxiety Scale, SF-36 Pain Scale, Multi-dimensional Assessment of Fatigue Scale, and the SF-36 Physical Function Component. With the exception of actigraphy (not collected due to budget), these measures, and hospitalization were assessed at T2 (6 months). Hospitalization was also elicited at 12 months.

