We enrolled 52 patients (planned $n = 40$); 48 completed treatment/follow-up in HS ($n = 29$) or HH groups ($n = 19$).²⁸ One HS patient did not complete due to a heart transplant. In the HH, non-completion was due to disappointment with randomization ($n=1$); loss to followup ($n=1$); and change to shift work ($n=1$). Eighty-eight percent of completers had 100% attendance. Inclement weather, damage to home, and death in family and were reasons for missed sessions that were made up by phone. Completers included 23 (47.9%) women, 15 (32.1%) African Americans, and 32 (66.7%) Whites and had NY Heart Class II or III HF. Age was $M = 61.9 \pm 13.3$ (HS group) and 55.2 ± 16.2 years (HH group) ($p = .12$). There were no statistically significant group differences at baseline on gender, NY Heart Class, comorbidity, symptoms or function. The apnea hypopnea index was $M = 7.44 \pm 5.5$ in participants not in treatment for SA. The proportion of patients using positive airway pressure (PAP) was equivalent between groups [$n = 5$ (17%) (HS) and $n = 3$ (16%) (HH)]. OTC or prescribed hypnotics were used 3 or more times/week by $n = 7$ (24%) (HS) and $n = 7$ (37%) (HH); 72% used ACEI/ARBs and 92% used beta-blockers, but there was no statistically significant difference between groups.

Satisfaction and acceptability were high and averaged 7.5-8.7 (scale: 0-10/10= high). Both groups rated scheduling, location, payment, study materials, interventionist effectiveness, and willingness to continue treatment as 8.5-9.5. There were no statistically significant differences between groups on ratings, and participants had no difficulty completing the measures. PAP users reported that CBT-I was helpful.

CBT-I had early and sustained effects. Insomnia severity improved in both groups (T1) and was similar to T1 at T2 (Table 2). The CBT-I effect was moderate-large at T1, with the mean decrease of > 7 points exceeding the criterion for improved function,¹⁰⁵ while the HH decrease was much smaller. In the HS, 93% improved across one or more levels of insomnia severity and only 2 deteriorated, while 68% of the HH group improved, and 26% deteriorated. At T1, only 48% of the HS had any insomnia ($ISI \geq 8$), compared with 68% of the HH group [$OR=0.43$, $CI_{95}=0.13, 1.45$]. The HS group improved at T1 on sleep quality, compared with HH. Self-reported (PSQI) and actigraph SE improved more at T1 in HS, and PSQI SE was similar at T2.

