Summary. We documented the high prevalence of chronic insomnia and its associations with disabling symptoms and functional performance in patients with stable HF and evidence-based HF disease management. Our pilot RCT revealed clinically and statistically significant early effects of CBT-I, a self-management intervention, compared with HF self-management education, on chronic insomnia, SE, and fatigue, while controlling for covariates. High acceptability and attendance, sustained effects, completion of all measures without burden, and promising effects on hospitalization are strong evidence of the impact of CBT-I on critical HF outcomes and the feasibility of our approach. The proposed fully powered RCT will establish a strong foundation for future research, including dissemination of CBT-I into HF disease management settings.

Table 2. Means, Standard deviations and Effect Sizes for Selected Outcomes at 2 Weeks (T1) & 6 Months (T2)

Variable	GROUP	Pre (T0)	Post (T1)	ES#	Post (T2)	ES#
		M (SD)	M (SD)		M (SD)	
Insomnia Severity	CBT-I (HS)	15.38 (4.79)	7.76 (5.21)	0.65	8.39 (4.44)	0.65
	Att Control (HH)	14.00 (4.33)	10.32 (5.30)		10.00 (4.34)	
Sleep Quality: PSQI *	CBT-I (HS)	9.43 (3.37)	7.25 (3.19)	0.46	7.65 (3.20)	0.02
	Att Control (HH)	9.78 (3.84)	9.32 (3.16)		7.77 (4.64)	
Slp Efficiency (%): (PSQI)	CBT-I (HS)	76.64 (15.78)	82.44 (14.45)	0.38	79.51 (18.74)	0.01
	Att Control (HH)	73.95 (14.18)	73.89 (11.81)		74.16 (18.95)	
Slp Efficiency (%) Actigraph \$	CBT-I (HS)	72.62 (10.25)	75.92 (8.35)	0.70	NA \$	NA
	Att Control (HH)	77.35 (7.09)	76.07 (11.03)		NA \$	
Fatigue	CBT-I (HS)	27.49 (13.16)	21.49 (10.61)	0.64	20.13 (11.52)	1.22
	Att Control (HH)	23.90 (11.20)	24.45 (10.00)		27.64 (10.43)	
Depression	CBT-I (HS)	13.76 (9.18)	12.17 (10.56)	0.06	8.87 (5.98)	0.16
	Att Control (HH)	16.74 (10.54)	14.63 (8.63)		(**) 14.00 (7.99)	
Anxiety	CBT-I (HS)	35.93 (11.61)	34.55 (13.73)	0.12	30.17 (9.29)	0.69
	Att Control (HH)	38.32 (13.68)	38.05 (10.73)		37.23 (12.69)	
SF36 Physical Function	CBT-I (HS)	26.72 (2.04)	27.21 (2.01)	0.26	26.96 (2.14)	0.23
	Att Control (HH)	27.11 (2.07)	27.30 (2.28)		27.82 (2.23)	

*higher score = poorer sleep quality; **favors attention-control group. ES# effect size; \$actigraph data not collected at T2; PSQI = Pittsburgh Sleep Quality Index.

APPROACH

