Sample Size. We performed power analyses to detect the effects of CBT-I on primary outcomes [insomnia severity, sleep quality (PSQI), self-reported (PSQI) and actigraph sleep efficiency (SE), and fatigue] with pilot data in which we randomized HF patients to CBT-I (HS) or attention control (HH). We calculated powers to detect differences in changes in outcomes from BL between the two groups to post-intervention (2 wks/T1) with 5% type I error.¹¹⁷ We also calculated powers with scenarios of high within-subjects correlations (Rho=0.6, 0.7, 0.8) for repeated measures during F/U (2 wks, 6, , 12 months) by assuming consistent effect sizes over time¹¹⁸ (Table 3). A sample of 100 independent participants per group will yield $> 90\%$ power to detect CBT-I effects on insomnia severity (ES=0.65), fatigue (ES=0.64), and PSQI sleep quality (ES=0.46) and power of 76.6% for PSQI SE (ES=0.38), but a power of 99.9% for actigraph-measured SE (ES=0.70). In scenarios based on within-subjects correlations of outcomes, we anticipate $> 95\%$ power for most outcomes and $> 80\%$ power for self-reported SE. Inclusion of 200 subjects (100/group) will permit sufficient power to detect the association between improved insomnia severity and symptoms [fatigue ($>99.9\%$, $r = 0.526$), depression (99.16%, $r = 0.299$), anxiety ($> 99.9\%$, $r = 0.510$), and pain (92.7%, $r = -0.238$)]. There will be 92.6% power to detect risk of hospitalization in participants with insomnia remission (9%), compared to no remission (27.8%). We will randomly assign 200 participants in 25-33 clusters of 6-8. Because we do not expect dependency among participants in the same clusters, we will not increase the sample for random cluster assignment.

We computed the power for estimating cost-effectiveness with Willan¹¹⁹ and Glick's¹²⁰ methods, based on an assumed alpha level of 0.05, expected cost difference of \$500, standard deviation for costs of \$2,000, expected correlation between costs and QALYs of -0.1, and willingness-to-pay of \$50,000 per QALY. The expected difference in QALYs, based on the pilot study, is estimated to be -0.33. Together, these values suggest that the sample of 100 subjects/group yields 89.7% power for detecting cost-effectiveness of CBT-I.

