A web link to the HIPAA-compliant online survey platform REDCap (<https://poa-redcap.med.yale.edu/>) will be emailed to heart failure patients who receive care by co-investigator, [name]. These patients and their email address will be identified through JDAT or [name]. These data will be stored in a secure, password protected Yale ITS-managed workstation and only be used to collect survey data about insomnia and to inform patients about the study.

Table 3. Powers to detect the expected effect sizes with a sample size of 100 per group

Outcome Variables	Effect Size	Two weeks post-intervention	Post-intervention measures (3, 6, 12 months)	
		Power	Rho (*)	Power
Insomnia Severity	0.65	99.2%	0.6	99.9%
			0.7	99.9%
			0.8	99.7%
Sleep quality: PSQI	0.46	90.2%	0.6	97.3%
			0.7	95.9%
			0.8	94.2%
Sleep Efficiency (%): PSQI	0.38	76.6%	0.6	89.5%
			0.7	86.3%
			0.8	83.0%
Sleep Efficiency (%): Actigraph	0.70	99.9%	0.6	>99.9%
			0.7	>99.9%
			0.8	>99.9%
Fatigue	0.64	99.5%	0.6	>99.9%
			0.7	99.9%
			0.8	99.8%

We will screen all participants who are not already adherent to positive airway pressure (PAP) for SA with the Apnea Risk Evaluation System (ARES) Unicorder (Watermark Medical, Inc.), a wireless recorder worn on the forehead <http://www.watermarkmedical.com/index.php>. (Appendix) ARES measures blood oxygen saturation (SpO2) and pulse rate (reflectance pulse oximetry), airflow (nasal cannula/pressure transducer), respiratory effort (pressure transducer - forehead venous pressure), venous volume (photo-plethysmography), snoring (acoustic microphone), head movement, and position (accelerometers). Pulse rate changes indicate arousals. Snoring changes indicate respiratory-related arousals. Forehead venous pressure is a valid measure of respiratory effort.¹²³ Head position indicates the positionality of obstructive events. ARES distinguishes REM from NREM with EEG, EOG and EMG electrodes at FP1 and FP2 (forehead). The apnea hypopnea index (AHI) is the sum of apneas and hypopneas/hour with 4% oxygen desaturation. Respiratory disturbance index (RDI) is the sum of apneas and hypopneas/hour with 1% desaturation and at least one arousal indicator.

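### Table 3's follow-up powers for the two PSQI primary outcomes correspond to four follow-ups, not three, and hold the two-week effect constant without addressing the pilot's near-zero 6-month figures

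*Combined protocol and SAP*

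**What the plan says.** **Power calculation.** The Sample Size section takes effect sizes from the pilot and calculates "powers to detect differences in changes in outcomes from BL between the two groups" at two weeks. It then calculates power "for repeated measures during F/U (2 wks, 6, , 12 months) by assuming consistent effect sizes over time", with within-subject correlations of 0.6, 0.7 and 0.8. For 100 per group, Table 3 gives:

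| Outcome | Effect size | Two weeks | Follow-up, rho 0.6 / 0.7 / 0.8 |
|---|---|---|---|
| PSQI sleep quality | 0.46 | 90.2% | 97.3 / 95.9 / 94.2% |
| PSQI sleep efficiency | 0.38 | 76.6% | 89.5 / 86.3 / 83.0% |

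The follow-up column is labelled "Post-intervention measures (3, 6, 12 months", so three visits. The SAP's repeated-measures model likewise has baseline plus three follow-ups.

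**Pilot.** The 6-month entries in Table 2 for the CBT-I arm, ending with the effect size, are "7.65 (3.20) 0.02" for PSQI quality and "79.51 (18.74) 0.01" for PSQI efficiency. The narrative on self-reported and actigraph efficiency says that they "improved more at T1 in HS, and PSQI SE was similar at T2", without saying similar to what. The pilot's self-report measures "were assessed at T2 (6 months). Hospitalization was also elicited at 12 months", so the pilot has no 12-month PSQI value.

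**Hypothesis 1a** expects "increased sleep quality, duration and efficiency that are sustained at 6, and 12 months".

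**The concern.** The follow-up powers are the plan's support for detecting PSQI effects beyond two weeks. They depend on the number of follow-ups and on the effect at each one. The number used does not appear to be the number planned. The effect used at 6 and 12 months is the two-week one, although the pilot that supplied it printed almost no between-group difference at 6 months for these two outcomes.

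For insomnia severity (0.65 at both times) and fatigue (0.64, then 1.22) the pilot is in line with a persisting effect. Actigraph efficiency was not measured at 6 months. The question is therefore specific to the PSQI outcomes. At stake is how a null PSQI result over follow-up would be read: Table 3 would present it as coming from a comparison with 83–97% power.

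**Working it through.** **Inputs.** 100 per group, 5% type I error, effect sizes and rho from Sample Size and Table 3. Sidedness is not stated; two-sided is assumed because it reproduces the printed two-week powers.

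**Formula** (time-averaged difference over m follow-ups, equal correlation):
- v = (1 + (m − 1)·rho)/m
- d = ES·√(50/v)
- power = Φ(d − 1.96) + Φ(−d − 1.96)

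**Step 1: reproduce the plan.** With m = 1 the powers are 90.19% and 76.64%, as printed. For follow-up:

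| | Printed | m = 4 | m = 3 |
|---|---|---|---|
| Quality | 97.3 / 95.9 / 94.2 | 97.31 / 95.86 / 94.16 | 96.70 / 95.32 / 93.75 |
| Efficiency | 89.5 / 86.3 / 83.0 | 89.46 / 86.26 / 83.01 | 88.06 / 85.18 / 82.29 |

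Example, efficiency at rho 0.6. For m = 4, v = 2.8/4 = 0.70 and d = 0.38·√(50/0.70) = 3.21, giving 89.5%. For m = 3, v = 2.2/3 = 0.733 and d = 3.14, giving 88.1%. All six printed values match m = 4 to the decimal and none matches m = 3. The largest gap is 89.5 − 88.1 = 1.4 points.

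Counting baseline as the fourth measure does not explain the match. The outcome is already change from baseline, and adding a measure with zero effect (average effects 0.345 and 0.285) gives 83.0/79.1/75.4 and 67.3/62.9/58.9.

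**Step 2: what the pilot's 6-month data say** (Table 2, unadjusted).
- Quality (lower is better): CBT-I improved by 9.43 − 7.65 = 1.78 points, against 9.43 − 7.25 = 2.18 at two weeks. Control improved by 9.78 − 7.77 = 2.01, against 9.78 − 9.32 = 0.46. CBT-I kept 1.78 of its 2.18 points; the gap closed mainly because control improved. The 6-month difference is 0.23 points in favour of control, so counting the printed 0.02 as a benefit is an assumption that helps the plan.
- Efficiency: CBT-I +2.87, control +0.21, difference 2.66 in favour of CBT-I. Divided by an SD of about 18.8 (6 months) or 15.2 (baseline), this is 0.14 to 0.18. The printed 0.01 does not follow from these means; it may be covariate-adjusted.
- Precision: with 29 and 19 patients the standard error of an effect size is √(1/29 + 1/19) = 0.295, so the 95% interval for 0.02 is −0.56 to 0.60. The 6-month n is not stated; 29/19 is assumed.

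**Step 3: power with three follow-ups and a reduced later effect.** With a share k of the effect kept at both 6 and 12 months, the average effect is ES·(1 + 2k)/3.

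| Assumed k | Quality, rho 0.6 / 0.7 / 0.8 | Efficiency, rho 0.6 / 0.7 / 0.8 |
|---|---|---|
| 100% | 96.7 / 95.3 / 93.8 | 88.1 / 85.2 / 82.3 |
| 75% | 88.6 / 85.8 / 82.9 | 74.4 / 70.7 / 67.2 |
| 50% | 71.6 / 67.9 / 64.4 | 55.2 / 51.7 / 48.6 |

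Using the pilot's 6-month effect, with the 12-month effect assumed:
- 12 months equal to 6 months: quality, average (0.46 + 2·0.02)/3 = 0.167, power 24–28%. Efficiency at 0.01, average 0.133, power 17–20%; at 0.14 to 0.18, averages 0.220 to 0.247, power 39–53%.
- Full return at 12 months: quality, average 0.313, power 66–74%. Efficiency at 0.01, average 0.257, power 50–56%; at 0.14 to 0.18, averages 0.300 to 0.313, power about 63–74%.

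For 80% power the average effect must be (1.96 + 0.84)·√(v/50) = 0.339/0.354/0.369. For efficiency this needs (3·average − 0.38)/2 = 0.32 to 0.36 at both later visits, or 84–96% of 0.38.

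**Step 4: insomnia severity row.** At the stated effect of 0.65 the formula gives 99.58% at two weeks (printed 99.2%) and 99.85–99.88% at rho 0.8 for m = 3 or 4 (printed 99.7%). An effect of about 0.62 gives 99.23% and, with m = 4, 99.74%. The row as a whole fits about 0.62.

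**The case against.** The strongest reply is that the constant effect is declared and that, granted it, the printed powers are right to within 1.4 points. That stands: what is left on the second count is a missing sensitivity range, not a calculation error.

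A reader might go further and infer that the pilot shows the PSQI benefit gone by 6 months, so that the trial is underpowered and N should rise. The documents do not support this. The pilot interval includes both 0.38 and 0.46, the CBT-I arm kept most of its own quality gain, and Table 2's means still favour CBT-I on efficiency. The 17–20% figure depends on a printed 0.01 that those means do not reproduce. This trial also adds monthly calls to 12 months; both arms receive them, so their net effect is unknown.

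The scenarios are also powers for a time-averaged difference. The SAP tests group by time with cube-root time and assesses sustained effects as non-inferiority to two weeks. Neither Table 3 nor the figures here give power for those tests.

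Finally, one might simply replace 99.2% with 99.6% for insomnia severity. That is not established, because the effect size used may be what differs.

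**Conclusion.** The point holds at moderate weight.

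- **Number of follow-ups.** The PSQI follow-up powers belong to four follow-ups. For the planned three they are 96.7/95.3/93.8% and 88.1/85.2/82.3%. This is a small discrepancy, and the plan's statement of more than 80% for self-reported efficiency survives under a constant effect. A leftover from a dropped 9-month visit is a plausible source, but that is inferred.
- **Constant effect.** This is the more consequential part. The assumption is stated but not set against the pilot's 6-month figures, and only rho is varied. PSQI efficiency has little margin: losing a quarter of the effect at both later visits takes it below 80% at every rho. PSQI quality tolerates that loss but not a loss of half.

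The size of any shortfall is unknown, because the true 6- and 12-month effects are unknown; hence a range and not a single figure. The results assume two-sided testing, equal correlation and 100 analysed per group. Insomnia severity, fatigue and actigraph efficiency stay at 99.8% or more for three follow-ups under the plan's own assumptions.

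**What to change.** Keep N unchanged and:

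1. Recompute Table 3 for three follow-ups.
2. For the two PSQI outcomes, either show follow-up power over a range of retained effects (for example 100, 75 and 50%), labelled as power for a time-averaged difference, or limit the power claim to the two-week comparison (90.2% and 76.6%). Add a sentence acknowledging Table 2's 6-month effects and saying whether the 0.01 is covariate-adjusted.
3. Reconcile the leftover visit text: the SAP's non-inferiority paragraph still names a 9-month assessment, and the human subjects section still counts five data collection periods.
4. Reconcile the whole insomnia severity row with its stated effect size of 0.65, not one cell.

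The cost is a table edit and a few sentences, with no added patients or data. The downside is that the stated PSQI follow-up power becomes less favourable.

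### Table 3's follow-up powers are for an effect averaged over visits; no power is given for the hypothesis that effects are sustained at 6 and 12 months

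*Combined protocol and SAP*

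**What the plan says.** Hypothesis 1a (Specific Aims) predicts "decreased insomnia severity and sleep latency and increased sleep quality, duration and efficiency that are sustained at 6, and 12 months". Hypothesis 1b makes the same kind of claim for symptoms, including fatigue.

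The Sample Size section gives two sets of powers for the five primary outcomes.

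- The first is for the arm difference in change from baseline "to post-intervention (2 wks/T1) with 5% type I error". For self-reported sleep efficiency it reports "power of 76.6% for PSQI SE (ES=0.38").
- The second uses "scenarios of high within-subjects correlations (Rho=0.6, 0.7, 0.8") and is obtained "for repeated measures during F/U (2 wks, 6, , 12 months) by assuming consistent effect sizes over time". Table 3 prints it under the heading "Post-intervention measures (3, 6, 12 months"), and the text summarises it as more than 80% for self-reported sleep efficiency.

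The text does not say how the follow-up visits are combined, and it does not call the second set the power for a sustained effect.

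The Data Analysis section, repeated in the SAP, has two routes that bear on durability. One is a repeated-measures mixed model with group, time and their interaction, in which time is continuous on a cube-root scale. The other is a non-inferiority comparison of the later outcomes with those at two weeks. No margin and no power are given for the second.

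**The concern.** Table 3 holds the only power figures for these outcomes during follow-up, so a reader will take its last column as the power behind the durability claim. That column is higher than the two-week column (83.0-89.5% against 76.6% for PSQI sleep efficiency). It therefore suggests that a lasting effect is easier to show than an immediate one.

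An average over all follow-up visits includes the visit two weeks after treatment, so an early effect can carry it with little left at 6 or 12 months. Two misreadings become possible: a significant average taken as evidence of durability, or a non-significant late difference taken as fading when power was limited. Sustained effect over twelve months is the trial's stated purpose.

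**Working it through.** **Inputs.** Sample Size section and Table 3: "A sample of 100 independent participants per group will yield" the stated powers, so n = 100 per arm; type I error 5%; effect size (ES) 0.38 for PSQI sleep efficiency and 0.46 for PSQI sleep quality, held constant over time; rho 0.6, 0.7, 0.8. The plan does not say whether the tests are one- or two-sided; two-sided reproduces its figures (one-sided would give 85.1% at one visit for ES 0.38).

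**1. One visit.** Power = Φ(ES·√(n/2) − 1.96).

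- ES 0.38: 0.38 × 7.071 = 2.687, so Φ(0.727) = 76.6%. Printed: 76.6%.
- ES 0.46: 0.46 × 7.071 = 3.253, so Φ(1.293) = 90.2%. Printed: 90.2%.

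**2. Average of m follow-up visits.** Power = Φ(ES·√(n/2) / √((1+(m−1)rho)/m) − 1.96). For ES 0.38, m = 4 and rho = 0.6, the variance factor is 0.70 and 2.687/√0.70 = 3.212, so Φ(1.252) = 89.5%.

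| Outcome | Printed (rho 0.6/0.7/0.8) | m = 4 | m = 3 |
|---|---|---|---|
| PSQI sleep efficiency | 89.5/86.3/83.0% | 89.5/86.3/83.0% | 88.1/85.2/82.3% |
| PSQI sleep quality | 97.3/95.9/94.2% | 97.3/95.9/94.2% | 96.7/95.3/93.7% |

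The printed rows match four follow-up visits to the decimal. The current schedule has three, although the SAP's non-inferiority sentence still names 9 months. Using three changes these rows by less than 1.5 points, so the visit count is not the issue here. Printed power falling as rho rises also fits an average.

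**3. Late visits.** At 12 months alone with constant ES, power is the single-visit figure. For both 6 and 12 months, it is the probability that two normal statistics, each with mean ES·√50 and with correlation rho, both exceed 1.96.

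| Outcome | 12 months alone | Both 6 and 12 months (rho 0.6/0.7/0.8) |
|---|---|---|
| PSQI sleep efficiency | 76.6% | 65.5/67.1/68.9% |
| PSQI sleep quality | 90.2% | 84.2/85.0/85.9% |

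Simulated t-tests for PSQI sleep efficiency at both visits gave 64.8/66.6/68.3%. For insomnia severity, fatigue and actigraph sleep efficiency, the both-visit power is 99.1% or more at the printed effect sizes.

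**4. What an average can hide.** Take ES 0.65 at the first follow-up visit and zero at 6 and 12 months. The three-visit mean effect is 0.65/3 = 0.217. The contrast is significant with probability Φ(0.217 × 7.071 / √((1+2rho)/3) − 1.96) = 43.2/40.2/37.7%.

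**5. A single group-by-cube-root-time slope.** The cube roots of 0, 3, 6 and 12 months are 0, 1.442, 1.817 and 2.289. Centred, they are −1.387, 0.055, 0.430 and 0.902, with sum of squares 2.926. With compound symmetry and ES in SDs of change, z = √(100/2.926) × Σ(centred time × ES).

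- Constant ES 0.38: 5.846 × 0.38 × 1.387 = 3.08, power 86.9%.
- ES 0.65 at 3 and 6 months and zero at 12: 5.846 × 0.65 × 0.485 = 1.84, power about 45%. The fitted arm difference is then largest at 12 months (about 0.25 SD, against 0.16 at 3 months), where the true difference is zero.

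**The case against.** The strongest reply is that no section requires significance at 6 months and again at 12. A reader might infer from the figures above that the true power for PSQI sleep efficiency is 66-69% and that the printed 83.0-89.5% is wrong. The documents do not support that. The printed figures are right for an averaged effect, the text presents them only as repeated-measures powers under a constant effect size, and the 76.6% single-visit figure is printed openly. The 66-69% belongs to a criterion that the plan does not set.

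The planned model also offers a test on which the more-than-80% statement survives. If the interaction is a single cube-root slope, its power at constant ES 0.38 is 86.9% under compound symmetry. It is 84.8/82.7/80.7% if the changes from baseline correlate at 0.6/0.7/0.8. The fitted 6- and 12-month differences are then multiples of one slope, so there is no penalty for requiring both.

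All of that stands. Neither planned route, however, establishes an arm difference at the late visits. The slope cannot isolate them (step 5). The non-inferiority comparison has no margin, so its power cannot be computed, and it does not say whether late outcomes are compared within the CBT-I arm or as arm differences. Within the arm, it could be met while the advantage over control disappears. In the pilot (Table 2; higher PSQI scores are worse), mean PSQI in the CBT-I arm went only from 7.25 to 7.65 between two weeks and six months. Control improved from 9.32 to 7.77, and the effect size fell from 0.46 to 0.02.

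The scope is also narrow: on the both-visit criterion only one of five primary outcomes falls below 80%.

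**Conclusion.** The concern holds as a mismatch between what was powered and what is hypothesised. Table 3's last column gives the power for an arm effect averaged over follow-up, and nothing in the plan gives the power for effects sustained at 6 and 12 months. If sustained means an arm difference in change from baseline at the late visits, PSQI sleep efficiency falls 6 to 13 points below the printed column at 12 months alone (83.0 − 76.6 = 6.4; 89.5 − 76.6 = 12.9). If both visits must be significant, it falls 14 to 24 points below (83.0 − 68.9 = 14.1; 89.5 − 65.5 = 24.0). PSQI sleep quality stays above 80% on either criterion, and the other three primary outcomes are barely affected.

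These figures assume the same effect size at every visit, 100 analysed per arm, independent participants, two-sided 5% tests at each visit and no false-discovery-rate adjustment. The constant effect size is granted for the argument; Table 2 reports 0.01 for PSQI sleep efficiency at six months. It would be wrong to describe Table 3 as miscalculated, or to present 66-69% as the plan's own power for the hypothesis.

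**What to change.** **Sample Size and Table 3.** Label the last column, and the more-than-80% sentence, as power for the effect averaged over follow-up. Add the power for the arm difference in change from baseline at 12 months and at both 6 and 12 months, stating the criterion as an assumption. For rho 0.6-0.8 these are 76.6% and 65.5-68.9% for PSQI sleep efficiency, and 90.2% and 84.2-85.9% for PSQI sleep quality.

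**Data Analysis and SAP.** Fit visit as a category in the repeated-measures model and estimate the arm differences in change from baseline at 6 and 12 months, with confidence intervals. Base any statement that an effect is sustained on those differences. An overall group effect, a single group-by-cube-root-time slope, or non-inferiority to two weeks should not support it alone.

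**Cost.** Wording changes and a few more model parameters. The stated follow-up power for the two PSQI outcomes becomes less favourable. No added participants, visits or data.

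### Table 3 gives insomnia severity (ES 0.65) less power than fatigue (ES 0.64), which cannot be right; at ES 0.65 the two-week figure should be 99.6%, not 99.2%

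*Combined protocol and SAP*

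**What the plan says.** The Sample Size section of the protocol sets the design for all outcomes together: "A sample of 100 independent participants per group will yield" more than 90% power for "CBT-I effects on insomnia severity (ES=0.65), fatigue (ES=0.64" and PSQI sleep quality (ES 0.46), calculated "with 5% type I error". It adds repeated-measures scenarios with "high within-subjects correlations (Rho=0.6, 0.7, 0.8" and an effect size held constant over time.

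Table 3 gives the results. Its first lines for the two outcomes read "Insomnia Severity 0.65 99.2% 0.6 99.9" and "Fatigue 0.64 99.5% 0.6 >99.9". In full:

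| Outcome | ES | Two weeks | rho 0.6 | rho 0.7 | rho 0.8 |
|---|---|---|---|---|---|
| Insomnia severity | 0.65 | 99.2% | 99.9% | 99.9% | 99.7% |
| Fatigue | 0.64 | 99.5% | >99.9% | 99.9% | 99.8% |

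The header of the repeated-measures columns lists three follow-ups (3, 6 and 12 months). Table 2, the pilot results, also gives 0.65 for insomnia severity, at both post-treatment time points.

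**The concern.** When sample size, significance level and correlation are fixed, power rises with the effect size. Table 3 has it the other way round for these two rows: insomnia severity has the larger effect but lower power at two weeks, at rho 0.6 and at rho 0.8, and the same printed power at rho 0.7. Either the printed effect size or the printed powers for insomnia severity are wrong.

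Insomnia severity is the first-listed primary outcome, so its planning assumptions are likely to be carried into the trial report. At stake is the internal consistency of the power table, not whether the trial is large enough.

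**Working it through.** **Inputs.** 100 per group, 5% type I error, effect sizes and correlations from the Sample Size section and Table 3. The text does not say whether the test is one- or two-sided. Two-sided is assumed here because it reproduces the other rows.

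**Two-week formula** (normal approximation): power = Φ(ES × √(100/2) − 1.96) = Φ(7.071 × ES − 1.96).

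| Outcome | ES | Computed | Printed |
|---|---|---|---|
| PSQI sleep quality | 0.46 | 90.20% | 90.2% |
| PSQI sleep efficiency | 0.38 | 76.64% | 76.6% |
| Actigraph sleep efficiency | 0.70 | 99.86% | 99.9% |
| Fatigue | 0.64 | 99.48% | 99.5% |
| Insomnia severity | 0.65 | 99.58% | 99.2% |

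Four of the five rows agree to the printed decimal. For insomnia severity, 7.071 × 0.65 − 1.96 = 2.636 and Φ(2.636) = 99.58%.

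**Could rounding or method explain 99.2%?** The smallest effect that rounds to 0.65 is 0.645, which gives 99.5%. A t-test at 0.65 gives 99.55% and a one-sided test 99.84%. About 90 per group would give 99.2%, but the other rows fit 100. The ordering does not depend on any of this: every value that rounds to 0.65 is at least as large as every value that rounds to 0.64.

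**Repeated-measures formula**, with m follow-ups: power = Φ(ES × √(100m / (2(1 + (m − 1)rho))) − 1.96).

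| Outcome (ES) | m = 3, rho 0.6 / 0.7 / 0.8 | m = 4, rho 0.6 / 0.7 / 0.8 | Printed |
|---|---|---|---|
| PSQI quality (0.46) | 96.7 / 95.3 / 93.7 | 97.3 / 95.9 / 94.2 | 97.3 / 95.9 / 94.2 |
| PSQI efficiency (0.38) | 88.1 / 85.2 / 82.3 | 89.5 / 86.3 / 83.0 | 89.5 / 86.3 / 83.0 |
| Fatigue (0.64) | 99.96 / 99.90 / 99.81 | 99.97 / 99.93 / 99.84 | >99.9 / 99.9 / 99.8 |
| Insomnia (0.65) | 99.97 / 99.93 / 99.86 | 99.98 / 99.94 / 99.88 | 99.9 / 99.9 / 99.7 |

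The PSQI rows identify m = 4. Fatigue fits either number, as does actigraph efficiency, which exceeds 99.9% throughout. Insomnia severity at 0.65 fits neither, and with either number it would be printed as >99.9 / 99.9 / 99.9.

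**What would give the printed insomnia row?** Under m = 4, the effect sizes that round to all four printed figures lie between 0.615 and 0.621, that is, 0.62 to two decimals: 99.23% at two weeks, then 99.95 / 99.87 / 99.74. Under m = 3, ES 0.62 gives 99.92 / 99.84 / 99.70, so the rho 0.7 cell would print 99.8, not 99.9, and only three of the four figures match.

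**Can the pilot table settle it?** No. The difference in mean change at the first follow-up is (15.38 − 7.76) − (14.00 − 10.32) = 3.94. If the effect size is that difference divided by the SD of change (an assumption, since the definition is not given), 0.65 implies an SD of 6.06 and 0.62 an SD of 6.35. Table 2 reports no SD of change.

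**The case against.** The strongest reply is that nothing depends on this. The largest gap is 99.58 − 99.2 = 0.4 percentage point, at power above 99%. The printed figures are too low for ES 0.65, so nothing is oversold. The text claims only more than 90% for insomnia severity, and more than 95% for most outcomes under repeated measures; both hold at 0.62 and at 0.65. All of that stands, and it makes this a minor point. It does not make the row correct.

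The reply also limits what may be inferred. A reader might conclude that the trial was really planned on 0.62, or that its planning effect is unknown. The documents do not support either. The value 0.65 is printed consistently in Table 2, the Sample Size text and Table 3, while 0.62 appears nowhere for insomnia severity and is only back-solved, with a full match that needs four follow-ups. Nor do the documents show that insomnia severity determined the sample size: it is one of five primary measures, and the lowest two-week power at 100 per group is 76.6%, for PSQI sleep efficiency.

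Finally, the number of follow-ups matters more for the PSQI rows than the insomnia slip does for its own row. Moving from four to three lowers PSQI efficiency at rho 0.6 from 89.5% to 88.1%, a difference of 1.4 points. A correction that touched only the insomnia row would leave that unexplained.

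**Conclusion.** The point holds as an internal error in Table 3. The insomnia severity row cannot belong to ES 0.65 while the fatigue row belongs to ES 0.64. The ordering argument needs only that both rows share the same sample size, alpha and correlations. The corrected values also assume a two-sided test, the normal approximation and a constant effect over time; they are the same after rounding for three or four follow-ups.

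The documents do not show which entry is out of date. The consistent printing of 0.65 favours correcting the powers, and only the pilot data can decide. The fit of the PSQI rows to four follow-ups suggests, without proving it, that the repeated-measures columns were computed for a schedule with one more visit than the header lists; the SAP's non-inferiority paragraph still mentions nine months. Neither the sample size nor the power claims in the text are affected.

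**What to change.** Check the pilot effect size for insomnia severity, then do one of the following:

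- If 0.65 is right, restate the row in Table 3 as 99.6% at two weeks and >99.9% / 99.9% / 99.9% at rho 0.6 / 0.7 / 0.8.
- If the pilot data show 0.62, correct the effect size in Table 2, the Sample Size text and Table 3.

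In either case, state beside Table 3 how many follow-up measures the repeated-measures columns assume, and compute every row on that number. If it is three, the PSQI rows become 96.7 / 95.3 / 93.7 and 88.1 / 85.2 / 82.3, and the fatigue and actigraph rows keep their printed values. At ES 0.62 with three follow-ups, the insomnia row would read 99.2% and 99.9 / 99.8 / 99.7. The text's claims of more than 95% for most outcomes and more than 80% for self-reported sleep efficiency still hold.

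The cost is a recalculation and an edit to one table, plus two further entries if the effect size changes. No design change is needed.
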